7.4. Biowaiver of bioequivalence test for other strengths

According to the official Mexican norm (NOM-177-SSA1-2013) if a product has more than one strength, in the same pharmaceutical form and shows acceptable in vitro dissolution testing of all strengths, a biowaiver is possible if the following requirements are met:

The proportionality (constant relationship) in the content of drug (s) and additive (s) in the qualitative-quantitative formula with respect to the drug was found. Proportionality must meet the following criteria (NOM-177-SSA1-2013):

- The drug (s) or additive (s) are in the same proportion between the different concentrations.
- The drug (s) or additive (s) are not exactly in the same proportion between the different doses, but the ratio of active ingredients relative to the total weight of the dosage form can vary up to 10% without any impact on the dissolution rate of the drug.
- For potency drugs, where the amount thereof in the dosage form is very low (less than 10 mg per tablet), and the total weight of the dosage form is equal at all doses, they could be proportionality if don't vary by more than 10% of the total weight of the dosage form.
- For immediate release, the coated components, colorings, flavorings and capsule shell should not be considered in the calculations to establish the proportionality of the formulas.
- The dissolution profile is similar between the bioequivalent strength of the test drug and the test drug with the strengths to exempt, which must be performed by an authorized third party.
- Sufficient scientific evidence is submitted to demonstrate that the drug exhibits linear pharmacokinetics in the range of concentrations applied.
- Manufacturing processes are validated.

8. Adverse Events

8.1. Warnings

Prior to the study drug's administration, information of the prescribing information related to the study side effects (approved by the Ministry of Health) should be considered. The Principal Investigator and the involved physicians in the study should know in advance the prescribing information.

8.2. Adverse Events Monitoring

Subjects should be carefully monitored with regards to the presence of adverse events. Adverse events should be established in terms of their seriousness, severity and causality with the study drug.

8.3. Observation Period for Adverse Events

Adverse events occurring from the signature of the informed consent form and until 14 days following the dosing in the second period of the study will be reported.

8.4. Adverse Events Definitions

8.4.1. Adverse Event

Any untoward medical event which might occur in a research subject during the clinical investigation stage of a drug or vaccine, but that not necessarily has a causality with it (NOM-220-SSA1-2016).

Adverse events related to the use of drugs in humans, whether related with it or not, include the following:

- ✚ An adverse occurring during the use of a drug in a professional setting.
- ✚ An adverse event occurring due to the abuse of drugs or illicit drugs.
- ✚ An adverse event occurring following the drug's intake stop.
- ✚ An adverse event where there is a reasonable possibility that the event occurred only as a result of the subject's participation in the study (e.g., serious or non-serious adverse event due to the antihypertensive drugs discontinuation during the wash-out phase) should be reported as an adverse event even if it is not related with the investigational product.
- ✚ Clinical onset of any failure of the expected pharmacological action.

If the event fulfills with the "serious" adverse event criteria should be recorded and reported as such.

8.4.2. Serious Adverse Event

A serious adverse event is any clinical onset occurring following the dosing of any drug, including vaccines, and that (NOM-220-SSA1-2016):

- ✚ Causes the subject's death.
- ✚ Is life-threatening for the subject when occurring.
- ✚ It is necessary to admit the subject at the hospital or extend his/her stay at the hospital.
- ✚ Causes permanent or significant inability or disability.
- ✚ Causes abnormalities or malformations in the newborn.
- ✚ Are considered medically important.

Some important medical events, even though they not produce death or are life-threatening, or require hospitalization, can be considered serious adverse events based on the appropriate medical opinion; or those which pose a risk for the subject, leading to medical or surgical intervention to avoid them. Example of those medical events include allergic bronchospasm which requires intensive treatment at the emergency room or at home; blood dyscrasias or seizures which do not lead the hospital admission or drug dependence or abuse.

Life-threatening means that the subject was, at the investigator's opinion, at immediate risk of death by the reaction when it occurred.

Disability means an important disorder in the person's ability to perform his/her daily activities.

8.4.3. Unexpected Adverse Reaction

An unexpected adverse reaction is an adverse reaction which nature or severity is not described in the product's prescribing information, nor in the documentation submitted for the marketing approval (NOM-220-SSA1-2016).

8.4.4. Exposure during pregnancy

If a female subject becomes pregnant during their participation in the study, the corresponding notification will be made as a serious adverse event. Follow-up will be mandatory throughout the pregnancy and until at least the first 6 months of life of the newborn (NOM-220-SSA1-2016).

Based on the subject's preference, follow-up can be done through telephone contact or medical consultation in the clinical unit, at least every two months during pregnancy and up to 6 months of life of the newborn or until the pregnancy is resolved (in case an abortion happens).

8.5. Causality of the Adverse Event with the Investigational Product

Establishment of the causality of the adverse events with the administered study drug is a clinical decision based on the available information when the adverse event occurred.

According to the causality assessment provided by the World Health Organization and the Uppsala's Monitoring Center, probabilistic characteristics are the following (NOM-220-SSA1-2016):

- ✚ **Certain:** clinical event, including laboratory tests abnormalities, which occur with a plausible temporary sequence with regards to the drug's dosing, and which cannot be explained by the concurrent disease, or by other drugs or substances. Drug's dechallenge response (withdrawal) should be clinically plausible. The event should be definitive from the pharmacological or phenomenological point of view, using, if necessary, the conclusive rechallenging procedure.
- ✚ **Probable:** clinical event, including laboratory tests abnormalities, which occur with a reasonable temporary sequence with regards to the drug's dosing and it is unlikely that it is attributed to the concurrent disease, or other drugs or substances; and that shows a clinically reasonable response to the drug's dechallenge. It is not necessary to have information about rechallenge to assign this definition.
- ✚ **Possible:** clinical event, including laboratory tests abnormalities, which occur with a reasonable temporary sequence with regards to the drug's dosing, but that can be explained by the concurrent disease, or by other drugs or substances. Information regarding the drug's dechallenge may be missing or unclear.
- ✚ **Unlikely:** clinical event, including laboratory tests abnormalities, which occur with an unlikely temporary sequence with regards to the drug's dosing which can be explained in a more plausible way by the concurrent disease, or by other drugs or substances.
- ✚ **Conditional or not classified:** clinical event, including laboratory tests abnormalities, reported as an adverse reaction, for which it is essential to get more data to make an appropriate assessment or which data are being analyzed.
- ✚ **Not evaluable or unclassifiable:** a report that suggests an adverse reaction which cannot be assessed due to insufficient or contradictory information and which data cannot be checked or completed.

8.6. Adverse Event Severity

Adverse events severity or seriousness should be classified as follows:

- ✚ Mild: occur with signs and symptoms easily tolerated that do not require treatment; they do not require hospitalization or its extension, and do not require that the causative drug is stopped.
- ✚ Moderate: interfere with daily activities (may cause work or school absence), without threatening the subject's life directly. They require pharmacological therapy and may not require that the causative drug is stopped.
- ✚ Severe: interfere with daily activities (may cause work or school absence). Require pharmacological therapy and the discontinuation of the causative drug.

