2.1. Secondary objectives

To assess the pharmacokinetics parameters of levothyroxine at a total dose of 600 µg (3 x 200 µg) of the test and reference drugs.

To assess the safety and tolerability of levothyroxine at a dose of 600 µg (3 x 200 µg) of the test and reference drugs.

The study objectives and endpoints are described in Table 2.

TABLE No. 2 Study Objectives and endpoints

Primary Objective	Endpoints

 To establish the bioequivalence between the new and approved levothyroxine's formulation in tablets of 200 µg (Eutirox® from Merck, S. A. de C. V.) in healthy volunteers for the marketing approval of the new formulation in all its strength. The lower strengths will be justified with the biowaiver criteria described in NOM-177-SSA1-2013 	
 Primary endpoints are baseline-adjusted $C_{max(a)}$ and $AUC_{0-t (a)}$ of levothyroxine (T4) in serum after dosing of 600 µg levothyroxine with either the test product or the reference product
Secondary objectives	Endpoints

 To assess pharmacokinetic parameters of levothyroxine To assess the safety and tolerability of levothyroxine 200µg for both test and reference products. 	
 Levothyroxine (T4): t_{max}, $t_{1/2}$, AUC_{0-t} and C_{max}. Safety assessments: Physical examination Vital signs (body temperature, blood pressure, Breathing frequency and pulse rate) Complete blood count; 4-panel chemistry; urinalysis; liver function tests; HIV, hepatitis B and C, and VDRL test; and qualitative urine test for illicit drugs, and pregnancy test for women. Thyroid profile. Electrocardiogram (ECG) Recording of Adverse Events (AEs)

3. Statistical hypothesis

H_0 : Drug A and drug B are not bioequivalent.

[figure not shown]
H_1 : Drug A and drug B are bioequivalent.

4. Investigational plan

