4.1. Experimental design and study plan

Single dose design will be used with 44 subjects in fasting state, two periods, two sequences, open-label, crossed in scheme blocks A-B and B-A, randomized, longitudinal, comparative and prospective, with a 35-day wash-out period between the two study periods. Treatment groups will be balanced, with the same number of subjects who will be randomly assigned to the study drug sequences of administration.

All data from participant subjects should be analyzed and included in the statistical analysis, if the fulfill with the established criteria.

Selection period (Screening)	Clinical phase			
	Period 1	Washout	Period 2	Clinical monitoring End of Study
30 to 2 days before the start of Period 1	From approx.12 hours pre-dose until 48 h sampling post- dose	At least 35 days	From approx. 12 hours pre-dose until 48 h sampling post- dose	At least 14 days after the dose in period 2

Subjects will be randomized to one of the 2 sequences by a randomization plan completed before first dosing

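### The severity scale in section 8.6 mixes intensity with treatment and drug discontinuation, so in two single-dose periods a grade can depend on the period and some adverse events fit no grade

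*Protocol*

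**What the plan says.** Section 8.6 of the protocol gives three grades.

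- *Mild*: easily tolerated, with no need for treatment, hospital care or stopping the drug.
- *Moderate*: interferes with daily activities, "without threatening the subject's life directly". It continues: "They require pharmacological therapy and may not require that the causative drug is stopped".
- *Severe*: interferes with daily activities in the same terms as moderate, and then: "Require pharmacological therapy and the discontinuation of the causative drug".

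Section 8.2 requires seriousness, severity and causality to be established for adverse events. Section 2.1 makes safety a secondary objective ("To assess the safety and tolerability of levothyroxine at a dose of" 600 µg of each product), and Table 2 lists the recording of adverse events among its endpoints.

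On the design, section 4.1 states: "Single dose design will be used with 44 subjects in fasting state". There are two periods and two balanced sequences. Section 4.4.2.3 sets 35 days between the doses. Section 8.3 has adverse events reported until 14 days after the second dose. Section 4.4.10 lets the investigator allow paracetamol for pain during the trial.

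**The concern.** A severity grade should say how intense an event was. Here the step from moderate to severe rests on what is done with the drug, and the step from mild to moderate rests partly on whether treatment is needed. Such a scale presupposes continuing treatment. In this trial each product is one intake of three tablets, so for much of the observation time there is nothing left to stop.

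What is at stake is the severity column of the adverse event summary for a stated secondary objective. If the scale cannot place an event, or places the same event differently in the two periods, the investigator has to improvise. An analysis plan can tabulate grades later, but it cannot restore an intensity that was never graded consistently.

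**Working it through.** The plan attaches no figure to this point. The check sets the three definitions against the design.

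**Step 1. What separates the grades.**

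| Element | Mild | Moderate | Severe |
|---|---|---|---|
| Interferes with daily activities | no (easily tolerated) | yes | yes |
| Requires drug therapy | no | yes | yes |
| Drug must be stopped | no | not necessarily | yes |
| Direct threat to life excluded | not stated | yes | no |

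Moderate and severe differ only in the last two rows. Degree of interference does not separate them.

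**Step 2. When discontinuation is available.** Each subject has two planned dosings, so 44 × 2 = 88 in all.

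- After the Period 1 dose, the only drug that can be stopped is the dose due 35 days later.
- After the Period 2 dose no further dose exists, yet events are reported for 14 more days. This covers 44 of the 88 planned dosings, or half.

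**Step 3. Literal grade by type of event.**

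| Event | Period 1 | Period 2 |
|---|---|---|
| Intense, interferes, needs drug therapy, not life-threatening | severe if the second dose is withheld, otherwise moderate | moderate only |
| Life-threatening, interferes, needs drug therapy | severe if the second dose is withheld, otherwise no grade | no grade |
| Interferes, needs no drug therapy | no grade | no grade |
| Easily tolerated, but treated (for example with paracetamol) | no grade | no grade |

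The first two rows depend on the single-dose design. The last two do not: they are gaps in the scale itself. The fourth row is foreseeable, because section 1.2.5 lists headache as a known reaction and section 4.4.10 provides for paracetamol for pain. It does assume that treatment given counts as treatment required. If the investigator judges that the paracetamol was taken but not needed, the event can still be mild.

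**Step 4. Effect between products.** Balanced sequences give 44 / 2 = 22 subjects each, so each product is planned for 22 dosings in each period. Any dependence of the grade on period falls equally on both.

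**Step 5. Dechallenge in section 8.5.** With the 6.2-day half-life from section 1.2.2.4, the fraction of a dose remaining at t days is 2^(−t/6.2):

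- at 14 days, 2^(−2.26) = 0.209, about 21 %;
- at 35 days, 2^(−5.65) = 0.020, about 2 %.

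Exposure therefore falls substantially after one dose, although not completely within the 14-day reporting window.

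**The case against.** The best reply is that section 8.6 speaks of what an event *requires*, not of what was done. An investigator can judge that an event is of a kind that calls for stopping the drug even when no tablet remains, and can then grade a Period 2 event severe. That reading is reasonable and it weakens the first two rows of step 3. But the text does not state it, so two investigators may read the scale differently. It also does nothing for an event that interferes but requires no drug therapy.

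Two further replies have some weight. Seriousness is defined separately in section 8.4.2 and drives the reporting times in section 8.7, so a grave event is not lost from reporting. Section 8.7 also asks for a detailed description, including therapy and consequence, which limits the loss of information. Neither supplies a consistent severity grade, and section 8.6 itself runs severity and seriousness together in its opening line.

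A reader might infer three stronger claims that the documents do not support.

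- *That no event can be severe.* Withholding the second dose is a discontinuation, and the judgement reading above covers Period 2.
- *That certain and probable causality are out of reach.* Section 8.5 asks of certain events: "Drug's dechallenge response (withdrawal) should be clinically plausible". It asks of a probable event that it "shows a clinically reasonable response to the drug's dechallenge". Both can be read as resolution while exposure falls. Sections 4.4.2.7 and 4.5.5 follow unresolved events beyond the final visit until they resolve, lose clinical relevance or are explained. Section 8.5 also treats causality as a clinical decision and has categories for events that cannot be classified.
- *That tolerability will look better than it was.* No endpoint or test in the protocol uses the grade, and a life-threatening event is barred from moderate, so it is not simply graded down. The supported description is inconsistent or unclassifiable, not systematically understated.

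**Conclusion.** The point holds for section 8.6 and is limited in size. The scale mixes intensity with treatment and action taken. Read literally, it can give the same event different grades in the two periods, can leave a life-threatening Period 2 event without a grade, and leaves two ordinary kinds of event without a grade in either period. Because section 8.2 requires severity to be established, this is a stated rule that works badly and not a detail left for later.

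The effect is confined to the descriptive safety summary. There is no bias between test and reference, provided dropout is similar in the two sequences, and no effect on the bioequivalence analysis. The number of events affected cannot be estimated, because the protocol gives no expected rate of moderate or severe events; the 44 Period 2 dosings are exposures, not events. The conclusion rests on the written definitions being applied as they stand and on the CRF, which is not shown, using the same three grades.

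**What to change.** In section 8.6, grade severity on functional interference alone:

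- mild: easily tolerated, no interference;
- moderate: some interference with daily activities;
- severe: prevents daily activities.

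Record the treatment given and the effect on the second dosing as separate CRF items, so that nothing now carried by the scale is lost. This closes all the gaps in step 3 and makes the grade independent of period.

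The cost is the wording of one section and one or two CRF fields, with no added visits, subjects or procedures. The downside is that some events may be graded higher than under the present text.

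A sentence in section 8.5 on how dechallenge is read after a single dose would be a helpful clarification, but it is optional.

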8.7. Adverse Events Documentation and Report

Any adverse event occurring during the study period should be fully recorded both in the subject's medical chart and in the Case Report Form.

Documentation should be supported by a record in the subject's medical chart. Laboratory tests abnormalities considered as clinically relevant, for instance, which cause the subject's withdrawal from the study and require therapy or cause apparent clinical signs in the subject, or that are considered relevant by the investigator, should be reported as an adverse event. All adverse events should be described in detail, including the subject's identity (name, age and sex), adverse event, suspected drug, reporter data, onset date and event's term and therapy, generic and distinctive name, dosage, route of administration, reason of prescription, event's consequence and important data in the medical history.

The report of adverse events will be the responsibility of the PPD

and will be made according to the standard operating procedure, code: PPD

and the Mexican Official Standard for the Pharmacovigilance Setting Up and Operations in Mexico, NOM-220-SSA1-2016. Therefore, reports from institutions or establishment which intend to or conduct research in human beings should be coded with reported clinical onset using the current MedDRA term. Timelines for reports submission to the National Center of Pharmacovigilance (CNFV) from the Federal Commission for the Protection against Sanitary Risks (COFEPRIS) in the country and to the Sponsor are as follows:

- ✚ Serious adverse event: up to 7 calendar days.
- ✚ Non-serious adverse event: report at the end of the study.
- ✚ Two or more serious events, similar in the same location, with the same drug and batch number: immediately, no later than 48 hours.

Report to the CNFV should be made by the Pharmacovigilance Officer at the PPD

in compliance with the NOM-220-SSA1-2016.

The ways to make the report to the Sponsor are the following:

Telephone:	PPD
Mobile:	PPD
E-mail:	PPD

According to the local law and regulations, adverse events should be reported to the appropriate Ethics and Investigation Committee, Investigation Committee and regulatory authorities.

9. Data Use and Publication

All data and results, and all rights and intellectual property for the data and results from this study will be property of Merck, S. A. de C. V. that can use the data in several ways, such as submitting them to government regulatory authorities or sending them to other investigators.

Although the Investigator is free to use the data obtained in the study for scientific purposes, he/she should discuss any publication with Merck, S. A. de C. V. in advance, and he/she should obtain the written consent from the Sponsor for the intended publication.

The Sponsor acknowledges the Investigator's right to publish the results once the study is completed. Anyway, the Investigator should send the paper's draft to be published or its summary to Merck, S. A. de C. V., 30 days in advance to the submission of the final version for publication.

This will be reviewed soon and approval will not be unnecessarily delayed. In case of disagreement between the Sponsor and the Investigators, publication content will be discussed to find an appropriate solution for both parties.

10. Management of Concurrent Events (Administrative and Medical)

10.1. Research Protocol Amendments

Research protocol amendments may be issued by the Principal Investigator in agreement with the Sponsor and vice versa, and should be approved by the Ethics and Investigation Committee and by the Investigation Committee. Administrative changes which do not affect the study design should be agreed and approved by the Sponsor, the Analytical Unit and the Principal Investigator. They should be submitted to the Ethics and Investigation Committee and to the Investigation Committee.

